Full study protocol and statistical analysis plan

Official Title of the study:

Serum Thiol/Disulphide Homeostasis level and its correlation with the severity of preeclampsia

Date of the document:

April 2019.

Contents:

- 1. Participant Flow
- 2. Baseline Characteristics
- 3. Outcome Measures
- 4.Endpoints of the study
- 5. Limitations and Strengths
- 6. Certain Agreements
- 7. Results Point of Contact

1. Participant Flow

Recruitment Details

This was an observational prospective cohort study conducted at Obstetrics and Gynecology Department of Cengiz Gokcek Obstetrics and Children's Hospital between April and October 2019. One hundred women will enrolled in the study in two groups. We will consecutively recruit 50 pregnancies complicated with preeclampsia, and 50 healthy pregnancies will select for the control group. All patients will gave their oral and written informed consent before their inclusion in the study.

Pre-assignment Details

We firstly will assess the recruited people to ensure meeting the inclusion and exclusion

criteria.

The inclusion criteria are made according to the official documents.

Arm/Group Information *

There are two groups in the study.

Arm/Group Title *

Preeclampsia group = Group A Control group= Group B

2. Baseline Characteristics

Frequency and percentage analysis will be used for some variables during data analysis. In addition, independent samples t-test (Student's t-test) will be used for comparison of the thiol/disulfide levels by the variable groups formed. The SPSS (IBM SPSS Statistics for Windows, Version 22.0. IBM Corp. NY, USA) statistical program will be used for all statistical calculations.

3. Outcome Measures

Every women in the study population will undergo obstetric ultrasound examination and fetalmaternal assessment will carry out by one of the authors. The obstetric anamnesis will obtain from all subjects. The dempograhic data like age, gravidity, parity, BMI and gestational age will record. Maternal venous blood samples will take for measurement of thiol and disulphide levels after the diagnosis of preeclampsia in outpatient clinic. These samples quickly will centrifuge at 1,500 g for 10 min, serum samples will separate and store at -80 C until the day of measurement. All patients with early onset preeclampsia will hospitalize. A betamethasone injection will administer immediately after hospitalization. The pregnancy will immediately terminate in emergencies arising from maternal or fetal causes. Otherwise, blood pressure will measured every four hours during periods of rest. Hypertension can will be confirmed within a shorter interval in patients with blood pressure ≥ 110 mm Hg diastolic and ≥ 160 mm Hg systolic in order to give timely antihypertensive treatment. Delivery will postpone for at least 24-48 hours if maternal/fetal status permit. A betamethasone injection for lung maturation (two dosages of 12 mg at 24 h intervals) will give within the said period. The control group's samples will obtaine during routine obstetrical care examination in the third trimester of pregnancy. Then these pregnant women will follow-up until delivery. All patients with late onset preeclampsia (LOPE) will also hospitalize and terminate. The control groups' samples will obtaine during the routine obstetrical care examination in the third trimester of pregnancy. Then these pregnant women were follow-up until the delivery. Both groups will compare in terms of maternal age, BMI, gravida, parity, week of gestation, systolic/diastolic blood pressure, total protein in spot urine sample, white blood cell (WBC) count, hemoglobin, platelet count, blood urea nitrogen, creatinine, liver function tests (AST, ALT), thiol, disulphide, and infant weight at delivery. Blood samples were separated by centrifugation for 10 minutes at 1500 g after clotting for 30 minutes at room temperature. The serum samples were subsequently stored in aliquots at -80°C prior to the analysis of thiol/disulphide levels. The contents of the native thiol (-SH) and total thiol (-SH + -S-S-) in the serum samples will measure using the reagent kits from Rel Assay Diagnostics (Gaziantep, Turkey). These spectrophotometric methods, developed by Erel and Neselioglu,(1) will assay in an auto-analyzer. The reducible disulfide bonds will first reduce to free-form functional thiol groups. The unused reductant, sodium borohydride, will consume and remove with formaldehyde, and all of the thiol groups, including the reduced and native ones, will measure after reacting with 5,5'-dithiobis-(2-nitrobenzoic) acid (DTNB). Half of the difference between the total and native thiols will yield the dynamic disulfide (-S-S) content.

4. Endpoints of the study:

The primary endpoint in this analysis is to evaluate thiol/disulfide levels in preeclampsia and address its relationship with its severity.

5. Limitations and strengths:

This study has a limitation that other oxidative parameters such as lipid hydroperoxide, total antioxidant status, total oxidant status and oxidative stress index were not measured.

6. Certain Agreements

The authors declare that they have no conflict of interest.

7. Results Point of Contact

Corresponding Author: [name], Cengiz Gokcek Public Hospital, Department of Obstetrics and Gynecology, Gaziantep/Turkey, [contact]

Adress: [name]

GSM: [contact]

Reference

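### Cases enter consecutively but controls by no stated rule, and the unadjusted t-test would not correct a resulting selection or gestational-age imbalance

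*Combined protocol and SAP*

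**What the plan says.** Section 1 (Participant Flow, Recruitment Details) sets the sampling: "We will consecutively recruit 50 pregnancies complicated with preeclampsia, and 50 healthy pregnancies will select for the control group". The total is fixed in the same paragraph: "One hundred women will enrolled in the study in two groups". It places the whole study in one department of one hospital between April and October 2019. On eligibility, section 1 says only this: "The inclusion criteria are made according to the official documents". The criteria themselves are not listed.

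Section 3 (Outcome Measures) gives the timing of blood samples. For controls: "The control group's samples will obtaine during routine obstetrical care examination in the third trimester of pregnancy". Case blood is taken after preeclampsia has been diagnosed, with no gestational window, and the section provides for both early- and late-onset cases. It also lists variables on which the two groups will be compared, among them maternal age, BMI, gravida, parity and week of gestation.

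Section 2 (Baseline Characteristics) names the independent-samples t-test for thiol/disulphide. No section mentions matching, stratification or covariate adjustment. Section 4 makes thiol/disulphide levels in preeclampsia, and their relationship with severity, the primary endpoint. The only limitation given in section 5 is that other oxidative markers were not measured.

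**The concern.** In a two-group comparison of a blood marker, the control mean contributes as much to the answer as the case mean. The case series has a rule that limits choice. The control series has no stated rule: no consecutive or random draw, no sampling frame, no matching, and no timing relative to cases within the study window. The 50 controls could therefore differ from the cases in age, BMI or gestational week for reasons unrelated to preeclampsia.

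Gestational week deserves separate mention because the sampling times differ by design. Controls are confined to the third trimester, whereas cases are sampled whenever they are diagnosed. Even a perfectly neutral choice of third-trimester controls would not by itself give the two groups the same distribution of weeks. An unadjusted t-test would attribute any resulting difference in thiol or disulphide to the disease. A shift in the other direction could hide a real difference.

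**Working it through.** **1. The two groups side by side**

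| Item | Cases | Controls | Where |
|---|---|---|---|
| Number | 50 | 50 | Section 1 |
| How chosen | Consecutive | Selected, rule not stated | Section 1 |
| Hospital and period | One hospital, April–October 2019 | Same | Section 1 |
| Time of blood sample | After diagnosis, no window given | Routine third-trimester visit | Section 3 |
| Disease onset | Early and late | Not applicable | Section 3 |
| Test for thiol/disulphide | Unadjusted t-test | Same test | Section 2 |

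Site and calendar window are shared. The selection rule and the gestational timing are not aligned.

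**2. What the plan would detect and what it would correct**

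The group comparison in section 3 could reveal an imbalance in age, BMI or week of gestation. Nothing in sections 2 to 4 says what would then be done about it.

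**3. How much a shift would matter at this sample size**

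The plan gives no alpha, power, SD or effect size, so it has no figure to reproduce. The following is an illustration on assumed inputs.

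- From section 1: n = 50 per group, so df = 50 + 50 − 2 = 98.
- Assumed: two-sided 5% test, no true disease effect, and a control mean displaced by b SD through selection or gestational timing.
- Noncentrality: ncp = b × √(n/2) = b × √25 = 5b.
- Rejection probability: P(|T| > t₀.₉₇₅,₉₈), where T is noncentral t with 98 df and noncentrality 5b.

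| Assumed shift b (SD) | ncp = 5b | False-positive rate |
|---|---|---|
| 0 | 0 | 5.0% |
| 0.1 | 0.5 | 7.9% |
| 0.2 | 1.0 | 16.8% |
| 0.3 | 1.5 | 31.8% |
| 0.4 | 2.0 | 50.8% |
| 0.5 | 2.5 | 69.7% |

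A normal approximation agrees within about 0.01.

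The same table shows the opposite risk. If a true difference of 0.5 SD were offset by a selection shift of 0.2 SD, the apparent difference would be 0.5 − 0.2 = 0.3 SD. The chance of detecting it would fall from 69.7% to 31.8%.

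**4. Which part of the endpoint is exposed**

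The preeclampsia-versus-control comparison uses the control mean and is exposed. A comparison of severity grades among the consecutively recruited cases does not use it and is unaffected by control selection.

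**The case against.** The strongest reply is that this is a reporting gap and not a decision to hand-pick controls. The English of the document is rough throughout, and one verb cannot show that controls are chosen at discretion. That stands: the text neither states nor excludes it.

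A reader might also connect the choice of controls with this phrase in section 3: "fetalmaternal assessment will carry out by one of the authors". That sentence concerns the examination of every woman in the study, cases and controls alike. It does not say who chooses controls. Nor does the plan allow any 50 women, since recruits are checked against inclusion and exclusion criteria that the document does not reproduce.

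A reader might infer that controls were enrolled in a block and so spent a different time in the freezer. Serum is stored at −80 °C until assay, but no order of enrolment is given and both groups share the same window. This is a possibility only.

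The planned comparison of age, BMI and gestational week is a real safeguard for detecting an imbalance. The 0.1 to 0.3 SD shifts are generic and would give the same rates in any t-test with 50 per group, so they do not measure the problem in this study.

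None of this supplies a control rule, aligns gestational week or adds an adjustment, so the narrower point remains.

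**Conclusion.** The point holds as a risk that the plan leaves open. Controls have no stated selection rule, their sampling time differs in kind from that of the cases, and the named test cannot correct an imbalance that the baseline comparison might reveal. Selection bias and gestational-age confounding in the preeclampsia-versus-control comparison cannot be excluded.

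It would go too far to say that bias is present, that it runs in a known direction, or that it undermines the whole primary endpoint. The documents give no size or direction for any shift, and the within-case severity question does not depend on control selection.

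The error rates rest entirely on the assumed shifts, a two-sided 5% level and 50 women per group. They show that modest shifts matter at this sample size, not that such shifts occur. The change should be made, because a poor choice of controls cannot be fully repaired after enrolment.

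**What to change.** - **Recruitment Details (section 1).** State the control rule. After each case, enrol the next consenting eligible healthy woman attending the same hospital's routine clinic, as close as feasible in gestational week to the case. Keep a log of women approached and women refusing. This makes the controls concurrent with the cases and removes choice from the process.
- **Analysis (section 2).** Compare thiol/disulphide between cases and controls with a linear model (ANCOVA) that includes gestational week at sampling, maternal age and BMI. Section 3 already records gestational age, age and BMI. It does not say at what time gestational age is recorded, so the time of sampling should be specified. With group and three covariates the model has five parameters including the intercept, which leaves 100 − 5 = 95 residual df. Adjustment works only where the gestational weeks of the two groups overlap, so the recruitment rule is needed as well.
- **Outcome Measures (section 3).** Reconcile third-trimester control sampling with any case diagnosed earlier. Such a case has no control of similar gestation under the present wording. A rigid matching band would meet the same obstacle, which is why closeness as far as feasible, with adjustment, is preferable.

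The number of women stays at 100 and no visits are added. The costs are somewhat slower control enrolment at unusual gestational weeks, a screening log, and a little more analysis work.

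### Does naming only Student's t-test, with no rule for unequal variances, put the thiol/disulphide comparisons at risk?

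*Combined protocol and SAP*

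**What the plan says.** The whole analysis text is in section 2 (Baseline Characteristics). It has one descriptive sentence, "Frequency and percentage analysis will be used for some variables during data analysis", one inferential sentence, "Student's t-test) will be used for comparison of the thiol/disulfide levels by the variable groups formed", and the software statement, "The SPSS (IBM SPSS Statistics for Windows, Version 22.0. IBM Corp. NY, USA) statistical program will be used for all statistical calculations". It mentions no variance check, unequal-variance version, transformation or rank-based alternative.

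The groups are set in section 1 (Participant Flow): "There are two groups in the study", with sizes fixed by "We will consecutively recruit 50 pregnancies complicated with preeclampsia, and 50 healthy pregnancies will select for the control group". Section 3 (Outcome Measures) lists thiol and disulphide among the variables on which these two groups are compared.

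Severity enters through section 4 (Endpoints): "The primary endpoint in this analysis is to evaluate thiol/disulfide levels in preeclampsia and address its relationship with its severity". The plan gives no severity categories, no subgroup sizes and no named test for this part. The study title speaks of a correlation with severity. Early and late onset disease appear in section 3 only in the management text, for example "All patients with late onset preeclampsia (LOPE) will also hospitalize and terminate", and not as analysis groups.

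**The concern.** Student's t-test in its textbook form pools the two variances. When the groups differ in both size and spread, the pooled standard error is wrong. It is too small if the smaller group is the more variable one, which gives too many false positives, and too large in the reverse case, which costs power.

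The plan leaves room for such a comparison. The test is assigned to whatever groups are formed, not just to cases and controls. Severity is part of the primary endpoint, and no other inferential method is named for it. The 50 cases are recruited consecutively, so nothing would make two severity subgroups equal in size. On that reading, half of the primary endpoint might be tested with a method whose error rate is uncontrolled, and replacing one phrase would put it right.

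**Working it through.** The plan states no alpha, SD, effect size or severity split, so it has no figure to reproduce. The 50 and 50 come from section 1. Everything else is assumed: two-sided alpha of 0.05, SD ratios up to 2, and splits of the 50 cases at 20/30, 15/35 and 10/40.

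**1. The documented comparison, 50 against 50.** With n per group, the pooled squared standard error is [(s₁² + s₂²)/2] × (2/n) = (s₁² + s₂²)/n. The Welch squared standard error is s₁²/n + s₂²/n, which is the same. The two t statistics are therefore identical and only the degrees of freedom differ.

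- Student: 50 + 50 − 2 = 98, critical value 1.984.
- Welch at a true SD ratio of 2: 49 × (1 + 4)² / (1 + 16) = 49 × 25/17 = 72.1, critical value 1.993.

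Using 1.984 where 1.993 applies gives an error rate of about 5.1%. Simulation with 200,000 normal datasets per setting agrees: Student 5.0 to 5.2% and Welch 4.9 to 5.1% for SD ratios from 0.5 to 2.

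**2. A hypothetical severity split of the 50 cases.** Compare what the pooled formula estimates with the true variance of the mean difference. Take 10/40 with SD 2 in the smaller group and 1 in the larger:

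- Pooled variance: (9 × 4 + 39 × 1)/48 = 1.5625.
- Pooled squared standard error: 1.5625 × (1/10 + 1/40) = 0.195.
- True variance: 4/10 + 1/40 = 0.425.
- Ratio of standard errors: √(0.195/0.425) = 0.678.
- Effective critical value: 2.011 × 0.678 = 1.363, a two-sided normal tail of about 17%.

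With the SDs swapped:

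- Pooled variance: (9 × 1 + 39 × 4)/48 = 3.4375.
- Pooled squared standard error: 3.4375 × 0.125 = 0.430.
- True variance: 1/10 + 4/40 = 0.200.
- Ratio of standard errors: √(0.430/0.200) = 1.466.
- Effective critical value: 2.011 × 1.466 = 2.947, a tail of about 0.3%.

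Simulated type I error of Student's test (normal data, 200,000 datasets per cell):

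| Split | Larger SD in smaller group, ratio 1.5 / 2 | Larger SD in larger group, ratio 1.5 / 2 | Equal SDs |
|---|---|---|---|
| 20/30 | 7.0% / 8.5% | 3.5% / 2.9% | 5.0% |
| 15/35 | 9.4% / 12.8% | 2.3% / 1.4% | 5.0% |
| 10/40 | 12.2% / 18.0% | 1.4% / 0.5% | 5.0% |

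Welch's test stayed at 4.9 to 5.1% in all these cells. An even 25/25 split gave 5.0 to 5.2% for Student, so both inequalities are needed.

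**3. What a blanket switch to Welch would cost.** With equal SDs and an illustrative effect of 0.9 SD, power for Student against Welch is 99.4 and 99.4% at 50/50, 86.4 and 86.1% at 20/30, 81.6 and 80.3% at 15/35, and 70.5 and 65.9% at 10/40.

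The plan says nothing about the shape of the distributions. With moderately right-skewed data (lognormal, log-SD 0.5) at 10/40:

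- Equal SDs: Welch about 6.3%, Student about 4.8%.
- SD ratio 2 (larger SD in the smaller group): Welch about 7.5%, Student about 18.4%.

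At 50/50 with the same skew, Student and Welch differ by about 0.1 percentage points or less.

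**The case for a change.** The strongest case for acting is that the switch is nearly free. One phrase changes, the estimated mean difference does not, and nothing is lost at 50/50. If severity is later compared between two uneven subgroups, Welch guards against an error rate two to three times nominal. Fixing the version beforehand also removes a choice between two p-values after the data are seen. The reference to groups formed from variables is broad enough to cover a severity split.

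Much of this stands. Student's is the only inferential test named, the figures reproduce, and for roughly normal data with clearly unequal spread in uneven groups Welch is the better test.

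What does not stand is the step from there to a defect in this plan. The title points to correlation and the endpoint to a relationship. If severity is analysed that way, or in three or more categories, a two-group Welch test does not address it. The equal-variance form is itself inferred from a parenthesis that may be only a generic label for the independent-samples test. Nor is Welch protective in every case: in a 10/40 split of skewed data with equal spread it is the slightly worse test. Renaming the test would also leave the severity part of the endpoint as undefined as it is now.

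**Conclusion.** No change follows. For the one comparison whose groups and sizes the plan states, 50 against 50, the two versions of the test give the same statistic and error rates within about 0.1 percentage points of each other, so the switch would alter no documented result.

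The distortion is real arithmetic, but it depends on a two-subgroup severity t-test, unequal subgroups and unequal SDs, none of which the documents state. Under those assumptions Student's error rate runs from about 0.5% to about 18%, in a direction that cannot be known in advance. With equal SDs it stays at 5.0%.

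This is missing detail that rests on a larger omission, the undefined severity categories and severity analysis. Whoever specifies that analysis has to choose its test anyway. If it turns out to be a comparison of two uneven subgroups, reporting the unequal-variance result would be a sensible ordinary choice, subject to the small power loss and the skewness caveat shown above. The conclusion assumes that recruitment ends close to the planned 50 and 50.

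### Do the two descriptions of serum preparation mean that case and control samples could be handled differently before the thiol/disulphide assay?

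*Combined protocol and SAP*

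**What the plan says.** Section 3 (Outcome Measures) covers collection and processing in one continuous paragraph.

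- **Case blood, collection:** "Maternal venous blood samples will take for measurement of thiol and disulphide levels after the diagnosis of preeclampsia in outpatient clinic".
- **Processing, first description, in the next sentence:** "These samples quickly will centrifuge at 1,500 g for 10 min, serum samples will separate and store", with storage at -80 C until measurement.
- **Control blood, collection:** "The control group's samples will obtaine during routine obstetrical care examination in the third trimester of pregnancy". A near-repeat of this sentence follows a little later. Neither states how the blood is processed.
- **Processing, second description, after the list of variables on which the two groups are compared:** "Blood samples were separated by centrifugation for 10 minutes at 1500 g after clotting for 30 minutes at room temperature". It continues: "The serum samples were subsequently stored in aliquots at -80°C prior to the analysis of thiol/disulphide levels".

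Section 2 (Baseline Characteristics) says that an independent samples t-test "will be used for comparison of the thiol/disulfide levels by the variable groups formed". Section 4 (Endpoints of the study) states: "The primary endpoint in this analysis is to evaluate thiol/disulfide levels in preeclampsia and address its relationship with its severity". No sentence says in so many words that Groups A and B are processed identically.

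**The concern.** The first processing sentence points back to case blood and asks for speed. The second asks for a half-hour wait and names no group. The control sentences carry no handling rule. A literal reader could therefore give cases one pre-spin interval and controls another.

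The two groups are also sampled on different occasions: after diagnosis for cases, and at a routine third-trimester visit for controls. A shared visit does not guarantee common handling. If the interval before centrifugation shifts the assay, the shift would go straight into the case-control difference, because the planned t-test is unadjusted. The measurement affected is the one the study exists to make.

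**Working it through.** **1. The two descriptions side by side (both in section 3)**

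| Step | First description | Second description |
|---|---|---|
| Samples covered | follows the case blood draw | no group named; follows the both-groups comparison |
| Before the spin | *quickly*; no interval, no temperature | 30 minutes of clotting at room temperature |
| Spin | 1,500 g, 10 min | 1500 g, 10 min |
| Product | serum | serum |
| Storage | -80 C | -80 C, in aliquots |

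Only the pre-spin step differs, and there the first description is silent on clotting rather than opposed to it. Serum is what remains after blood has clotted, so a clotting step is implied. The second description supplies its length. Both can be followed at once: clot for 30 minutes, spin promptly, freeze.

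**2. Scope of the second description.** It speaks of blood samples without restriction. It comes directly after the sentence listing what both groups are compared on, thiol and disulphide included. It leads into the assay steps (kits, analyser, reduction, DTNB reaction), none of which is split by group. No separate control procedure appears anywhere.

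**3. Signs of duplicate drafting.** The same paragraph gives the control-sampling sentence twice almost word for word, and repeats the follow-up sentence. The second processing description is in the past tense and the first in the future. This fits one procedure written down twice.

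**4. What a between-group difference would require.** Three things must all hold: the sentences describe different procedures; the 30-minute step is withheld from some or all case blood; and the interval shifts the assay. The text supports neither of the first two, and the documents contain nothing on the third.

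**5. Size, if a shift is simply assumed.** The plan has no power calculation, alpha, SD or effect size, so there is no figure of its own to reproduce. Inputs: 50 per group (section 1, Participant Flow); assumed two-sided alpha 0.05; no true difference; handling shift *s* in SD units, tracking fully with group.

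- SE of the standardised difference = √(2/50) = 0.2.
- P(reject) = 1 − Φ(1.96 − s/0.2) + Φ(−1.96 − s/0.2).
- For s = 0.2: 1 − Φ(0.96) + Φ(−2.96) ≈ 0.170.

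| s (SD) | 0 | 0.1 | 0.2 | 0.3 | 0.4 |
|---|---|---|---|---|---|
| False positives | 5.0% | 7.9% | 17.0% | 32.3% | 51.6% |

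The noncentral t with 98 df gives nearly the same: 5.0, 7.9, 16.8, 31.8 and 50.8%. If only half of one group were handled differently, the mean shift would be s/2, so 0.4 SD would act roughly as 0.2 SD (about 17%). If both routes were mixed equally within both groups there would be no bias, and the added variance at 0.4 SD would be 0.4²/4 = 0.04, or 4%. For scale, the difference detectable with 80% power is (1.96 + 0.84) × 0.2 ≈ 0.56 SD.

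These figures apply to any systematic shift in a 50 versus 50 comparison. On the natural reading of section 3, s = 0 and the rate stays at 5%.

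**The case for a change.** The strongest reply is that, even if the second description covers everyone, case blood then falls under two instructions, and the reader must decide which governs. A shift well below the 0.56 SD that the study could detect would still distort the main comparison, and one sentence would remove the doubt.

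Part of this stands. The wording is untidy, and common handling has to be inferred. But to put the two instructions in conflict, *quickly* must be read as cancelling a clotting step that serum requires. A laboratory given a general word and a specific time would follow the specific time. Merging the sentences would improve the prose without altering what is done. Logging draw and freeze times, or capping the time from draw to freezer, is reasonable good practice, but nothing in the documents shows that timing matters for this assay, so neither is needed to make the plan sound.

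**Conclusion.** The duplication is real, but it is a drafting slip and not a planned difference in handling. Followed as written, the section gives one procedure for all 100 women: 30 minutes of clotting, a prompt spin at 1,500 g for 10 minutes, and storage at -80 C. On that reading handling adds no bias to the case-control comparison.

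The severity comparison, made among cases, is likewise unaffected, and it would be unaffected even if every case were spun at once. It could be disturbed only if handling varied among cases in step with severity, which nothing suggests.

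This rests on two judgements: that the unrestricted second description applies to both groups, and that *quickly* means promptly once the blood has clotted. No size of bias can be derived from the documents. Merging the two sentences would be a courtesy to the reader; the analysis does not depend on it.

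### Cases and controls are bled under different timing rules with no matching stated, and no step is planned to correct the unadjusted marker comparison for gestational age at sampling

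*Combined protocol and SAP*

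**What the plan says.** Participant Flow (section 1) sets the groups: "We will consecutively recruit 50 pregnancies complicated with preeclampsia", and "50 healthy pregnancies will select for the control group". It gives no matching rule.

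Outcome Measures (section 3) sets the timing. For cases: "Maternal venous blood samples will take for measurement of thiol and disulphide levels after the diagnosis of preeclampsia in outpatient clinic". Early-onset cases are expected ("All patients with early onset preeclampsia will hospitalize"), and late-onset cases are mentioned too, but no onset cut-off is given. For controls: "The control group's samples will obtaine during routine obstetrical care examination in the third trimester of pregnancy". That instruction appears twice, each time without a week.

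The same section covers gestational age: "The dempograhic data like age, gravidity, parity, BMI and gestational age will record", and later "Both groups will compare in terms of maternal age, BMI, gravida, parity, week of gestation", followed by blood pressure, urine protein, blood tests, the markers and infant weight. It does not say to which date the week refers.

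The only named test for the markers is under Baseline Characteristics (section 2): "independent samples t-test (Student's t-test) will be used for comparison of the thiol/disulfide levels by the variable groups formed". No regression, stratification or other adjustment appears. The primary endpoint (section 4) covers marker levels in preeclampsia and their relation to severity.

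**The concern.** The sampling week follows a different rule in each group. Disease onset sets it for cases; the timing of a routine antenatal visit sets it for controls. If the markers drift with gestation and the two rules give different average weeks, the t-test credits the drift to preeclampsia. If the drift runs the other way, it hides a true difference. The comparison exposed is the one behind the primary endpoint.

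Comparing weeks between groups can show a gap but does not remove it from the marker comparison. The plan names no action if a gap is found.

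**Working it through.** The plan has no figure to reproduce: it gives 50 v 50 but no alpha, power, effect size or SD. What follows is an illustration.

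**Assumed inputs (none from the documents).** Two-sided alpha is 5% and residual marker SD is 1. The third trimester is weeks 28-40, and early onset is before week 34. Early cases are 30% or 50% of the group, sampled uniformly from week 24 or 28 to week 34; the rest are sampled uniformly over 34-39. Controls are uniform over 28-40, 34-40 or 28-34. The marker trend is 0.05, 0.10 or 0.15 SD per week. At 0.15 the within-case correlation with week would be 0.41-0.55, which is strong.

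**Step 1: gap in mean week.** Mean case week = early share × midpoint of early range + late share × 36.5.

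- 30% early from week 28: 0.3 × 31 + 0.7 × 36.5 = 34.85
- 30% early from week 24: 0.3 × 29 + 0.7 × 36.5 = 34.25
- 50% early from week 28: 0.5 × 31 + 0.5 × 36.5 = 33.75
- 50% early from week 24: 0.5 × 29 + 0.5 × 36.5 = 32.75

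Control means are 34 (weeks 28-40), 37 (34-40) and 31 (28-34). The absolute gaps are therefore 0.25-1.25, 2.15-4.25 and 1.75-3.85 weeks.

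**Step 2: spurious difference = trend × gap.** With spread controls the largest is 0.15 × 1.25 = 0.19 SD. With clustered controls the range is 0.05 × 1.75 = 0.09 SD to 0.15 × 4.25 = 0.64 SD.

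**Step 3: approximate check.** For a shift b and marker SD 1, the t-test has 98 degrees of freedom and non-centrality b × √(50/2) = 5b. Rejection rates are 7.9% for b = 0.1, 31.8% for 0.3, 50.8% for 0.4 and 84.4% for 0.6.

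**Step 4: simulation, no true effect, 20,000 runs per setting.**

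| Controls sampled at | t-test false positives | Week comparison significant |
|---|---|---|
| Weeks 28-40 | 4-11% over all trends | about 29% at the 1.25-week gap |
| Weeks 28-34 or 34-40 | 7-18% at 0.05; 12-51% at 0.10; 20-82% at 0.15 SD/week | about 100% in 7 of 8 settings, about 83% in the eighth |

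The 82% needs every extreme input at once. With zero trend there is no bias. Rates below 5% arise because the number of early cases was held fixed; letting it vary gives about 5-12.5% for spread controls.

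**Step 5: masking.** With a true difference of 0.6 SD, an opposing trend of 0.10 SD per week and controls at 34-40, t-test power is 12-46%. Without a trend it is 84-85%.

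**Step 6: what linear adjustment achieves.** With a straight trend it holds false positives at 4.7-5.3%, as it must, since the same model generates the data. Poor overlap is where it fails. Take an effect of 0.9 SD in early and 0.3 SD in late cases, half early and no trend. The true average is 0.5 × 0.9 + 0.5 × 0.3 = 0.60. The adjusted estimate is 0.38-0.40 with controls at 34-40 and 0.69-0.78 with controls at 28-34. With overlapping controls it is 0.55-0.59.

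**The case against.** The strongest objection is that the plan already contains a warning light. If the week compared is the week at sampling, the settings with high false-positive rates are those where the week comparison is almost always significant. A false-positive t-test together with a non-significant week comparison occurs in at most about 5% of studies in any setting, and in about 2% or fewer where controls cluster.

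A reader might infer that the week comparison would usually miss the problem, since a 1.25-week gap is non-significant in about 71% of studies. But that figure belongs to a setting with spread controls and false positives of only 6-11%. It must not be set beside the 20-82% rates. This objection stands. What it leaves is that no step follows a flagged imbalance.

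A reader might also infer that the recorded week could just as well be the week of delivery. The list does not favour that: it places the week among examination-time measurements and attaches delivery only to infant weight. Examination or enrolment is the more natural reading, though it is not stated.

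Two further points stand. Clustered controls are an assumption, and the documents describe no such pattern. The plan also says its inclusion criteria follow official documents that are not reproduced, so gestational limits or a matching rule may exist there. The finding concerns this document only.

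**Conclusion.** The point holds as a gap in the analysis plan. As written, the unadjusted t-test cannot separate a preeclampsia effect from a difference in sampling week. A large imbalance would probably be seen, but no correction is planned.

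The size is unknown. The documents give no marker trend, no distribution of sampling weeks and no onset cut-off, so every rate above rests on assumption: near nominal to about double with spread controls, and anywhere from 7% to 82% with clustered ones. A reader might infer that the comparison is biased; the documents do not show that, because they establish neither a trend nor a gap. Confidence is high that the correction is missing and low on how much it matters. It should be fixed because the primary comparison is exposed and the repair is cheap.

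**What to change.** 1. Record gestational age at blood sampling, under that name, for every woman.
2. Choose controls from routine attendees so that their sampling weeks overlap the cases', frequency-matching on week bands fixed in advance where practical.
3. For each marker, pre-specify one primary preeclampsia-control comparison, adjusted for gestational age at sampling in a linear model, with a 95% CI. Report the planned t-test beside it.
4. Report how many cases fall outside the controls' week range, with a sensitivity analysis limited to the overlapping weeks. If overlap is poor, limit the conclusion to those weeks, because a linear model does not repair poor overlap when the effect differs by onset or severity.

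The cost is SAP wording, one defined data field and some scheduling of controls, with no extra women or assays. For a 0.6 SD effect and no trend, power moves from 84-85% (t-test) to 83-85% (adjusted) when weeks overlap. The loss is larger when they do not: adjusted power is 70-78% with controls at 34-40 and 64-82% at 28-34. Restricting to overlapping weeks also has a price: if cases are sampled from week 24 and no control before week 28, 12-20% of cases drop out and the question narrows, so that analysis is a sensitivity analysis.

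If recruitment has closed, controls cannot be rechosen, but items 1, 3 and 4 remain possible wherever gestational age on the sampling date can be recovered.
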